OBJECTIVES	
Primary objective: To determine the efficacy of the TALI Train Program in improving attention in children with Acquired Brain Injury
 
Secondary Objectives: (a) To compare attentional deficits between children with ABI, TBI and typically developing children; (b) To identify factors which predict improvements in attention following the completion of the TALI Train program and to determine whether improvements in attention resulting from completion of the TALI program are translated into improvements in other domains including mathematics ability, working memory, and social skills

DESIGN	
The study design will be a 2 (conditions; control and attention training) x 4 (time points: pre-intervention, post-intervention, 3 month follow up, 6 month follow up) design. The study will comprise a blinded, parallel group, randomised control trial.
 
Data will be analysed using Latent Growth Curve Modelling.

OUTCOMES	
Primary outcomes:
 
The primary outcome will be change in cognitive attention as measured by the Test of Everyday Attention for Children second edition (selective and sustained attention) and experimental paradigms of attentional control (interference control and response inhibition) between the intervention and control group at post-training.
 
Secondary outcomes:
 
Secondary outcomes will include behavioural attention (inattention and hyperactivity), measured using the SWAN; working memory measured using the Corsi block-tapping task (visuospatial working memory) and a digit span test (auditory working memory); social skills, measured using the Paediatric Evaluation of Emotions, Relationships, and Socialization (PEERS); and mathematics ability measured using the WIAT-II.

STUDY DURATION	24 months
INTERVENTIONS	TALI Train Program (www.talihealth.com.au)
NUMBER OF PARTICIPANTS	80 participants; 40 per group (2 groups)
POPULATION	80 Victorian children aged 4-9 years, with Acquired Brain Injury, residing in Victoria (both Metropolitan and Regional Areas).

GLOSSARY OF ABBREVIATIONS

ABBREVIATION	TERM
ABI	Acquired Brain Injury
ADHD	Attention Deficit Hyperactivity Disorder
ANOVA	Analysis of Variance
CRF	Case Report Form
HREC	Human Research Ethics Committee
MCRI	Murdoch Children's Research Institute
NHMRC	National Health and Medical Research Council
PEERS	Paediatric Evaluation of Emotion, Relationships and Socialisation

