3.2 Secondary objectives

The secondary objectives of this study are:

- to investigate whether there are differences in the types of attentional deficits found in typically developing children, when compared with children with an ABI.
- to identify factors which predict improvement in attention in children with ABI who complete the TALI attentional training program, and

- to determine whether improvements in cognitive attention transfer to improvements in other domains including mathematical ability, working memory and social functioning in children with ABI who complete the TALI Train program.

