5.2.1 Inclusion criteria

Participants must meet all of the following criteria to be enrolled in this study:

- Is between the ages of 4 years and 9 years 11 months at the time of randomisation.
- Has a primary diagnosis of an ABI.
- Has an attentional deficit as determined by the Conners EC/3 parent rating scale. Children who score above 60 (t-score: elevated range) on either of the subscales relating to inattentive behaviour (inattention: DSM Inattentive) of the Conners 3, or on the inattention/hyperactivity subscale of the Conners EC will be deemed eligible for inclusion in the trial.
- At least 6 months has passed since the time of injury, or in the case of ABI due to cancers, since the conclusion of treatment (including chemotherapy).
- Has a legally acceptable representative capable of understanding the informed consent document and providing consent on the participant's behalf.

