8.3 Screening

Stage 1 Screening

The first stage of screening will be undertaken by researchers based on information gained from the VPRS database and audit of medical records and will be based on the inclusion criteria outlined in section 5.2.1. The parents of children who meet the inclusion criteria will be contacted via the means outlined in section 5.3. Once informed consent for participation is received by the researchers, families will be invited to participate in the second stage of screening.

Stage 2 Screening

The second stage of screening will be conducted online. Parents/guardians of participants will be sent an email inviting them to participate in the screening process. Parents will be asked to complete a demographic and medical questionnaire, and the Conners 3 or Conners EC depending on the age of the child. Both the Conners 3 and Conners EC will be administered and scored via the online Conners platform. The Conners is used to measure ADHD symptoms and in this study, will be used to determine whether children meet the criteria of an attentional deficit needed to participate in the study. An attentional deficit will be defined as a t score >60 on either of the two inattention subscales of the Conners 3, or on the inattention/hyperactivity subscale of the Conners EC.

If the screening assessments have not been completed after a period of two weeks, a member of the research team will contact participants to follow up. This will entail one documented reminder email, and one follow up Short Message Service (SMS) or phone call. If a period greater than 2 weeks has passed from the first reminder contact date then participants will be recorded as having 'incomplete' screening and they will not be contacted further.

Stage 3 Screening

Following completion of the second stage of screening, researchers will assess eligibility for the study based on the exclusion criteria listed in section 5.2.2.

In cases where children meet all other eligibility criteria, children who have not undergone IQ testing post injury and within the last two years, will be asked to complete either the WASI or the WPPSI (dependent on age). The WASI/WPPSI will be administered by a trained member of the research team at MCRI. Should the child be unable to attend MCRI, an offer will be made to conduct this assessment at the child's school or within the family home.

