13.2.3 Methods of analysis

Primary outcome measure

To meet the primary objective of the study, the four primary outcome measures: response inhibition, interference control, selective attention, and sustained attention as measured by the Anticipated Response task, Child ANT, and TEA-Ch 2 respectively, will be analysed using Latent Growth Curve Modelling (LGCM) using a multigroup approach. An alpha level of .05 and two-tailed tests will be used for this analysis. LGCM will be conducted through R. Participants will be compared to their own baseline at each of the three subsequent testing time points, and further comparisons will be made between time points (e.g. 5 week follow up and 3 month follow up, 5 week follow up and 6 month follow up). Participants in the TALI program group and the active contact group will also be compared at each time point. LGCM will allow for baseline ability to be taken into consideration.

Secondary outcomes measures

To meet the secondary objective of determining whether improvements in cognitive attention transfer to improvements in other domains including mathematics ability, working memory and social functioning in children with ABI who complete the TALI attentional training program, further LGCM will be used as described above with the secondary outcome variables listed in section 9.2.

Additional analysis

To meet the secondary objective of identifying factors which predict improvement in attention in children with ABI who complete the TALI attentional training program, LGCM will be used. Predictor variables will be obtained through data collected from the demographic screening survey including age at time of injury, type of injury, length of time since injury, severity of attentional deficits and socio-economic background, as well as from data obtained through assessment measures relating to motivation, sleep, mental health and family functioning.

To meet the final secondary objective of investigating whether there are differences in the types of attentional deficits found in typically developing children, when compared with children with ABI, children's scores on the Connor's EC/3 will be compared using an independent samples, two-tailed ANOVA with an alpha level of .05

Data on typically developing children will be obtained from previous study database, whereby participants consented to their de-identified data being used for further research.

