13.3 Interim Analyses

Screening data will be analysed to give an indication of different attention profiles across children with ABI and TBI. No further interim analyses will be conducted and researchers will be blinded to group allocation throughout the trial including analyses.

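### The objective on types of attentional deficit is tied to an independent-samples ANOVA on Conners scores, which tests level of deficit and cannot by itself establish a difference in type

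*Protocol*

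**What the plan says.** Section 3.2 lists as a secondary objective "to investigate whether there are differences in the types of attentional deficits found in typically developing children" relative to children with ABI. Section 13.2.3 (Additional analysis) repeats it in almost the same terms ("To meet the final secondary objective of investigating whether there are differences in the types of attentional deficits found in typically developing children") and assigns it one method: "children's scores on the Connor's EC/3 will be compared using an independent samples, two-tailed ANOVA", at alpha .05. The typically developing data come from an earlier study's database, whose size is not given.

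Two other places bear on the meaning. The synopsis words the objective without the notion of type: "To compare attentional deficits between children with ABI, TBI and typically developing children". Section 13.3, on the other hand, speaks of patterns: "Screening data will be analysed to give an indication of different attention profiles across children with ABI and TBI".

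The Conners subscales are named only where eligibility is defined. Section 5.2.1 names two Conners 3 subscales, inattention and DSM Inattentive. Section 8.3 sets the cut-off on "either of the two inattention subscales of the Conners 3, or on the inattention/hyperactivity subscale of the Conners EC". Section 13.2.3 does not say which scores enter the ANOVA.

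**The concern.** A difference in type means that the pattern across attention domains differs between groups: one group is relatively worse in one domain than in another. In statistical terms that is a group-by-subscale question. An independent-samples ANOVA has a between-group factor only, so each such test asks whether mean scores are equal, which is a question of severity.

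Running it once per subscale does not turn it into a test of pattern. If all domains are raised equally, several subscales may be significant although the profile is the same. If one subscale is significant and another is not, that is not a test that the two differ.

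At stake is the interpretation of one secondary objective. A general elevation in children with ABI could be read as a different kind of deficit, and if a single averaged score is used, a real difference in kind could be missed.

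**Working it through.** **The plan's own figures.** The protocol gives no sample size or power for this comparison. Its only calculation is in section 13.1, for the trial itself. With noncentrality f²·N·m/(1+(m-1)ρ), m = 2 and ρ = .5, it reproduces: f = .4, N = 40 gives 8.53 and power .812; f = .25, N = 98 gives 8.17 and power .808. It does not bear on the Conners comparison.

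**Inputs.**
- From the protocol: 80 children with ABI (section 5.1); two-sided alpha .05 (section 13.2.3).
- Assumed: T-score SD 10; two subscales with correlation r = .6 (range .4 to .8); 80 comparison children (range 40 to 160).

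**Formulas.** With two groups the ANOVA F equals t², so power follows from the noncentral t with δ = Δ / [SD·√(1/n₁+1/n₂)]. For 80 versus 80 the root is √(2/80) = 0.158.
- Single subscale: SD 10, standard error 1.581.
- Average of two subscales: SD = 10·√((1+r)/2) = 8.94, standard error 1.414.
- Group-by-subscale contrast (difference between the two subscales): SD = 10·√(2(1-r)) = 8.94, standard error 1.414. It equals the previous SD only because r = .6.
- At least one of two subscales: simulation, 40,000 runs per setting.

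**Rejection rates, r = .6, 80 versus 80.**

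| True difference (subscale 1, 2) | Averaged score | One given subscale | At least one subscale | Group-by-subscale |
|---|---|---|---|---|
| +5, +5 (same profile) | δ = 5/1.414 = 3.54; 94% | δ = 5/1.581 = 3.16; 88% | 95% | 5% |
| +3, +3 (same profile) | δ = 3/1.414 = 2.12; 56% | δ = 3/1.581 = 1.90; 47% | 62% | 5% |
| +3, -3 (different profile) | δ = 0; 5% | δ = 1.90; 47% | 82% | δ = 6/1.414 = 4.24; 99% |

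**Range.**
- For r from .4 to .8 at 80 versus 80, under +5/+5 the averaged score rejects in 96% to 91% and at least one subscale in 97% to 93%.
- Over the same r, under +3/-3 at least one subscale rejects in about 78% to 86% and the interaction in 93% to nearly 100%.
- With 40 or 160 comparison children (r = .6), the averaged score under +5/+5 rejects in 82% or 98%.
- Under a uniform shift the interaction test stays at its nominal 5% throughout.

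**Reading.** Per subscale, the ANOVA is reasonably sensitive to a profile difference but not specific to one, because severity alone triggers it at least as readily for the +5 shift. On one averaged score it is neither specific nor sensitive.

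**The case against.** Several points on the other side are sound.

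- The synopsis wording is answered by a test of level, and types could be taken to mean which domains are impaired relative to typical children, which domain-by-domain comparisons address. This stands as a reason to reconcile the wording. It does not remove the mismatch, because section 13.2.3 attaches the ANOVA to the wording with types.
- A reader might infer that the protocol will declare any significant ANOVA to be a difference in type. No section contains that rule. What can be said is that no other test is named for the objective.
- A reader might also infer that the analysis cannot answer the objective in either direction. That holds only for a single averaged score, which the protocol does not specify. Per subscale, a +3/-3 difference is flagged about 82% of the time.
- It is tempting to say that the Conners EC cannot separate inattention from hyperactivity and that the two forms are pooled. The combined EC subscale is named only for eligibility, and the EC/3 shorthand in section 5.2.1 means whichever form suits the child's age. The documents do not show which EC scores will be analysed.
- The choice of subscales could be left to a separate analysis plan. That is fair for the detail, but here the protocol fixes a test, its sidedness and its alpha, and that test does not match the objective.

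Nor is this the entry rule in another guise ("Children who score above 60 (t-score: elevated range) on either of the subscales relating to inattentive behaviour"). That rule would enlarge a level difference if enrolled children form the ABI group, which the protocol does not say. The mismatch would remain in an unselected sample.

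**Conclusion.** The point holds as a mismatch between a stated objective and the one test fixed for it. Under the assumptions given, a uniform 5-point elevation rejects in about 95% of runs on at least one subscale, or about 94% on an averaged score, with no difference in type. The loss of sensitivity (5% against about 99% for the interaction) is confined to an averaged score. The percentages depend on the assumed SD, correlation, comparison-group size and shift. That a uniform shift rejects the ANOVA null and leaves the interaction at 5% does not. The comparison is secondary and non-randomised, and no treatment-effect estimate is touched; the change is worth making but not critical to the trial.

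**What to change.** In section 13.2.3, replace the independent-samples ANOVA with a mixed (profile) model on Conners T-scores: group between children, subscale within child. Take the group-by-subscale interaction as the test of type and report the group main effect separately as severity. Fit it separately for Conners 3 and Conners EC.

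Name the subscales in advance. They must cover distinct domains and be held in the comparison database. The two Conners 3 subscales used for entry are not enough: both measure inattention, so an interaction on those two alone would say little about type.

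If a form has no separable subscales available, limit its conclusion to level of deficit and align the objective in sections 3.2 and 13.2.3 with the synopsis.

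Cost: a change of wording and a check of what the comparison database holds. The Conners is already scored online at screening, so no new assessment of trial participants is implied if the subscale scores are kept. The downside is fewer children in each form-specific comparison.

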5.2.3 Definitions

Acquired Brain Injury

An acquired brain injury (ABI) is defined as damage to the brain that occurs from 28 days after birth. ABI can be classified as traumatic brain injury (TBI) and non-TBI dependent upon causative factors such as trauma, brain tumours, vascular insults, and infections; it does not include injuries induced by birth trauma, or degenerative or congenital brain abnormalities (Emanuelson et al., 2003).”

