5.4 Consent

Prior to performing any study specific procedure (including screening procedures to determine eligibility), a signed consent form will be obtained for each participant. Written consent will be provided by the legal guardian, as all participants will be under 12 years of age.

All potential participants will be provided with an information pack, by mail or email, including a Plain Language Statement, a consent form, a child information sheet and a reply paid envelope (if required). The Plain Language Statement will include information detailing the purpose of the study, the procedures used, the risk, benefits, and other relevant information. Consent will be voluntary and free from coercion. Upon receipt of the signed consent form, contact will be made with the guardians of potential participants by a member of the research team to confirm interest in participating in the study, to address any questions raised from the information pack and explanatory statement, and to ensure that participants understand the purpose, extent and possible risks associated with their involvement in the study. The researcher that conducted the consent discussion will also sign the informed consent form. If a consent form has not been returned after a period of 2 weeks, researchers will contact participants to follow up. A copy of the consent form will be given to the participant or their legally acceptable representative and the fact that the participant has been consented to the study will be documented in the participant's research file.

For participants who do not meet the eligibility criteria for the study, de-identified electronic data will be retained for use in future studies, where consent has been provided by the guardian to do so. A database of ineligible participants will be maintained for the duration of the study to ensure that they are not contacted by any other member of the research team during recruitment should the child be identified through more than one method (eg. EMR audit and VPRS database).

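### The comparison of Conners scores between ABI and typically developing children uses the scale on which enrolled ABI children were selected, with no matching rule stated for the comparison group

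*Protocol*

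**What the plan says.** Section 3.2 of the Protocol sets a secondary objective: "to investigate whether there are differences in the types of attentional deficits found in typically developing children, when compared with children with an ABI". Section 13.2.3, under the additional analyses, fixes how it is met: scores on the Conners "EC/3 will be compared using an independent samples, two-tailed ANOVA with an alpha level of .05". The typically developing children come from the database of a previous study. Section 13.2.3 names no subscale, does not say which children with ABI contribute, and does not say how the database children were selected.

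The Conners is also the entry instrument. Section 5.2.1 admits "Children who score above 60 (t-score: elevated range) on either of the subscales relating to inattentive behaviour" of the Conners 3, "or on the inattention/hyperactivity subscale of the Conners EC will be deemed eligible for inclusion in the trial". Section 8.3 repeats the rule: "An attentional deficit will be defined as a t score >60 on either of the two inattention subscales of the Conners 3", or on the single Conners EC subscale.

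Three other places bear on who is in the ABI group:
- Section 13.2.1 states that all children enrolled in the trial are analysed.
- Section 5.4 states that, for children who prove ineligible and where the guardian consents, "de-identified electronic data will be retained for use in future studies".
- Section 13.3 plans an analysis of screening data to describe attention profiles in ABI and TBI. It does not mention typically developing children.

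The synopsis words the objective differently: "To compare attentional deficits between children with ABI, TBI and typically developing children". Section 5.2.3 states that "ABI can be classified as traumatic brain injury (TBI) and non-TBI".

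**The concern.** The outcome of this comparison is the variable used to select one of the two groups. A child with ABI whose inattention scores are ordinary cannot enrol. If the ABI group is the enrolled children, its distribution on the selecting subscales is cut off from below by design. Setting it against a group without that cut-off produces a difference even if brain injury has no effect on attention.

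Restricting attention to the type of deficit rather than its level does not avoid this. Selection shifts the selecting subscale most and shifts the others in proportion to their correlation with it, so the entry rule alone can produce what looks like an inattentive profile. A significant result could then be reported as evidence about ABI when it reflects the eligibility criterion.

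**Working it through.** **The plan's own figure.** The Protocol gives no sample size or effect size for this comparison. Section 13.1 (40 to 98 participants) concerns the treatment comparison. It reproduces from its listed parameters and has no bearing here.

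**Inputs from the Protocol.** Threshold T above 60 (5.2.1, 8.3); one selecting subscale for the Conners EC and either of two for the Conners 3 (5.2.1); 80 children with ABI (5.1); two-tailed test at .05 (13.2.3).

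**Assumptions.** T-scores are normal with mean 50 and SD 10 in both populations, so there is no true difference. The two Conners 3 inattention subscales correlate at .5 to .9. The comparison group has 20 to 80 children and was not selected on the Conners.

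**1. Conners EC, one selecting subscale.** The cut-off is a = (60 − 50)/10 = 1. With φ(1) = 0.2420 and 1 − Φ(1) = 0.1587, λ = 0.2420/0.1587 = 1.525.
- Mean of selected children: 50 + 10 × 1.525 = 65.25, a gap of 15.25 points.
- SD of selected children: 10 × √(1 + 1.525 − 1.525²) = 4.46.
- Standardised difference: 15.25/√((100 + 4.46²)/2) = 1.97.
- Simulated rejection with 80 ABI children against 20, 40 or 80 others: 100%.

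**2. Conners 3, either of two subscales.** For correlation r, the gap on each subscale is 10 × (1 + r) × φ(1) × Φ(√((1 − r)/(1 + r)))/P, where P is the probability that at least one subscale exceeds 60.

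| r | P | Φ term | Gap (points) |
|---|---|---|---|
| .5 | .255 | .718 | 10.2 |
| .7 | .233 | .663 | 11.7 |
| .9 | .202 | .591 | 13.5 |

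For r = .5: 10 × 1.5 × 0.2420 × 0.718/0.255 = 10.2. Simulated rejection across these correlations, with 80 ABI children against 20 to 80 others, is 99.3% to 100%.

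**3. A Conners subscale not used for selection.** If it correlates ρ with a single selecting subscale, the induced gap is ρ × 15.25. Simulated rejection at 80 against 80:

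| ρ | Gap (points) | Rejection |
|---|---|---|
| 0 | 0 | 5% |
| .1 | 1.5 | 16% |
| .3 | 4.6 | 83% |
| .5 | 7.6 | 99.9% |
| .7 | 10.7 | 100% |

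**4. With selection removed or matched.** At 80 against 80 with no true difference, rejection is 5.2% when neither group is selected and about 6% when both are held to T above 60. The excess comes from unequal selection.

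**The case against.** The strongest reply is that the premise is not written down. Section 13.2.3 does not say that the ABI group is the enrolled children. The Conners is completed at stage 2 screening, before eligibility is settled (8.3), so scores of screened-out children exist, and section 13.3 plans to use screening data for attention profiles. The statement in 13.2.1 most naturally governs the randomised comparison, and 5.4 permits later use of ineligible children's data without barring present use. The database children may also have been selected for inattention, in which case most or all of the artefact could disappear.

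Part of this stands. A reader might infer that a false positive is guaranteed, or that screened-out children are reserved exclusively for later research. The documents do not support either: the first depends on how the comparison children were chosen, which is not stated, and 5.4 contains no such restriction. Near-certain rejection is also shown only for the selecting subscales.

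It does not clear the plan. Nothing in the Protocol widens the ABI group for this test or applies the threshold to the database. Section 13.3 ties screening data to ABI and TBI alone, and the only population statement refers to enrolled children. The instrument and the test are already fixed, so this is more than a detail awaiting a later document.

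A reader might also infer from the synopsis that overlapping ABI and TBI groups break the independence of the ANOVA. They do not: sections 3.2 and 13.2.3 describe two disjoint groups, ABI and typically developing. The overlap is a wording fault.

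**Conclusion.** The concern holds conditionally. If the ABI group is the enrolled children and the typically developing children were not selected on the Conners, a type I error of nominally 5% becomes about 99% to 100% on the selecting subscales. The spurious gap is about 15 points for the Conners EC and 10 to 13.5 points for each Conners 3 inattention subscale. On other subscales the false rejection rate lies between 5% and 100%.

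These sizes rest on the assumed T-score distribution, the assumed correlations and an assumed comparison group of 20 to 80. The first condition is the reading the text best supports; on the second the Protocol is silent. The defect is confined to one non-randomised secondary comparison, but under these conditions that comparison cannot answer its objective on the selecting subscales. It should be corrected.

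**What to change.** Amend section 13.2.3 in one of these ways, in order of preference, and name the subscales to be compared:

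1. Define the ABI group for this objective as all children with ABI who completed the stage 2 Conners, whatever their score, subject to consent covering this use.
2. Otherwise apply the same T above 60 rule to the typically developing group, and interpret the result as a comparison of profiles among children with elevated inattention.
3. If neither is possible, report Conners profiles within ABI descriptively with the selection caveat, and do not test ABI against typically developing children on the selecting subscales.

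In each case, state how the database children were selected.

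The cost is wording and a check of the consent text; stage 2 screening already collects the scores. The first option does not remove all selection: the recruitment material in Appendix F invites families whose child currently has attention difficulties, and that limitation must be stated with the result.

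Separately, reconcile the synopsis objective with sections 3.2, 5.2.3 and 13.2.3, since TBI is a subset of ABI. This is a wording correction and does not alter the two-group test.
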